8.2 Statistical Analysis Plan

Proposed Data Analysis Primary Objectives

Objective response rate and progression-free based on RECIST 1.1 criteria (RC) will be estimated with 90% confidence intervals. The objective response rate (ORR) will be estimated by the proportion of subjects with the best response of complete response (CR), or partial response (PR) by RC, with corresponding exact 90% confidence limits being reported.

Proposed Data Analysis Secondary Analysis

The progression-free survival (PFS) will be measured from the initial date of the study treatment to the date of documented tumor progression using RC, or the date of death in the absence of tumor progression. PFS will be estimated by the Kaplan-Meier method with Greenwood 90% confidence intervals

Within-patient changes in CD8+ cells will be measured in tumor tissue and in peritoneal fluid at weeks 1,8, and 12. Mixed linear models will be used to estimate changes from baseline.

An assessment of the association among immune parameters, and ORR will be conducted. Endpoints for analysis include (CTL, NK- and Th1 cells) in the peritoneal fluid and resected residual tumor mass The panel of immune parameters will be tested for association with objective response with the Jonckheere-Terpstra test for trend by ordering response 1-4 for PD, SD, PR and CR, respectively. Significant association will be adjusted for initial tumor grade, and the interval between initial diagnosis of OC and protocol accrual. To guard against false positive results, the estimated false discovery rate will be calculated by the method of Benjamini and Hochberg (J. R. Statist. Soc. B Vol 57, No 1, 289-300, 1995).

HCC 18-087 Version Dated 5-20-2021

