3.0 OBJECTIVE(S) & HYPOTHESIS(ES)

3.1 Primary Objective(s) & Hypothesis(es)

(1) **Objective:**

This phase II trial will consist of up to 45 evaluable patients to specifically define the clinical efficacy and impact on immunologic efficacy endpoints of IP cisplatin/rintatolimod and IV pembrolizumab. Primary clinical efficacy endpoint will be objective response rate by RECIST

6

1.1 criteria at 13 weeks (CT imaging at 7 weeks and 13 weeks) as compared to historical controls. The trial schema encapsulates a trial design similar to our recent phase I SPORE trial (UPCI 11-128/NCT02615574, [name] - Clinical PI; [name]- Translational PI) in which intraperitoneal cisplatin and rintatolimod was well tolerated and induced favorable immune response on interim analysis.

The strategy of combining pembrolizumab with IP cisplatin/rintatolimod is to induce cell death and cell damage of the peritoneal tumor implants with chemotherapy followed by locoregional and systemic modulation of innate and adaptive immune effectors to further promote immune clearance of remaining tumor.

Objective/Pathologic Response

Imaging will be performed at baseline, two weeks after cycle 2 and cycle 4 for objective responses by RECIST 1.1 criteria. Imaging will again be performed 4-6 weeks after completion adjuvant chemotherapy for baseline post treatment. Between 2 months after successful completion of the trial, the IP port will be removed laparoscopically. During the IP port removal, a second-look treatment effect evaluation and biopsy for pathologic response will be performed.

Disease Progression

Progression during trial will be assessed by iRECIST. If there is confirmed progression prior to interval surgery, patients will not undergo interval surgery, just IP port removal and biopsy after confirmed progression by iRECIST. Patients will be followed for 3 years or until recurrence after completing treatment to determine time to progression (TTP), ratio of progression-free interval (PFI) as compared to their initial PFI, and survival will be a secondary efficacy endpoint. Follow-up data will be used to estimate progression-free and overall survival at 3 years.

Biological Endpoints

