The primary endpoint is the objective response rate (rate of CR+PR by RECIST 1.1) at 13 weeks. Based on Ten Tije and Wils et al, the intent-to-treat objective response rate for IP cisplatin alone in platinum-sensitive recurrent ovarian cancer was approximately 45% 51 . An increase from 45% to 65% among response-evaluable patients would be of sufficient interest to warrant further study of the addition of rintatolimod and pembrolizumab in the presence of an acceptable safety profile. An optimal Simon two stage design with $\alpha = \beta = .10$ has been selected that will require 20 patients in the first stage and 25 in the second. In the first stage, 12 patients must have a response (PR or CR) in order to continue to the second stage. If the trial continues to the second stage and accrues 25 more patients and there are 25 or more patients with an objective response among the total of 45 treated, the study will be considered successful at demonstrating increase efficacy compared to cisplatin alone. The probability of early termination if the response rate is 45% is .59.

Continuous Monitoring of RLTs during the Study

Subject safety will be monitored continuously using Bayesian methods. If the posterior probability is .80 or greater that 30% or more of treated subjects experience a treatment related RLT as defined above, the RLT rate would be unacceptable and the study will be suspended pending review by the DSMC. This posterior probability will be calculated from the study's accumulating data and a weakly informative prior distribution. If π denotes a random variable representing the proportion of subjects who will experience a treatment related RLT, we assume π has a beta distribution with parameters a = 1.2 and b = 2.8 which assumes a mean of 30%. The table below describes the number of RLTs per number of treated patients that would trigger suspension. The table also shows the posterior probability that the RLT rate exceeds 33% and the binomial probability associated with the decision for an assumed 33% RLT rate.

Table 8: Number of RLTs per Number of Patients Treated Needed to Trigger Suspension

Subjects	Treatment-Related RLTs	$PP(\pi > 30\%)*$	$Pr(X \ge r p = .30)$
6	4	.903	.070
9	5	.904	.099
12	6	.890	.118
15	7	.880	.131
17	8	.903	.105
20	9	.896	.113
23	10	.891	.197
26	11	.886	.125
29	12	.883	.129
32	13	.880	.133

35	14	.877	.135
38	15	.876	.137
41	16	.874	.138
44	17	.873	.139

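### Section 8.2 estimates the primary response rate from best response with no time limit, while Sections 3.1 and 8.1 fix it at 13 weeks; read literally, scans after debulking could count

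*Combined protocol and SAP*

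**What the plan says.** Section 8.1 states: "The primary endpoint is the objective response rate (rate of CR+PR by RECIST 1.1) at 13 weeks". Section 3.1 agrees and names the scans: "at 13 weeks (CT imaging at 7 weeks and 13 weeks) as compared to historical controls".

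Section 3.1 also separates the scans by purpose. For response: "Imaging will be performed at baseline, two weeks after cycle 2 and cycle 4 for objective responses by RECIST 1.1 criteria". For the later scan: "Imaging will again be performed 4-6 weeks after completion adjuvant chemotherapy for baseline post treatment".

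Section 8.2, under the heading for the primary objectives, says the rate is "estimated by the proportion of subjects with the best response of complete response (CR), or partial response (PR) by RC", with exact 90% limits. It sets no time limit and does not refer back to 13 weeks.

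The schedule around surgery is as follows:
- The week-13 scan precedes interval surgery (Tumor Imaging During the Study, numbered 7.1.2.6.1).
- Debulking is at weeks 15-16 in the flow chart (6.1). Sections 2.1 and 3.3 leave it to the treating physician, and 2.1 says it takes out whatever tumor is visible.
- Scans follow 4-6 weeks after treatment ends and then every 12 weeks until progression.
- One group is kept out of surgery: "If there is confirmed progression prior to interval surgery, patients will not undergo interval surgery".

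**The concern.** The estimator in 8.2 and the endpoint in 8.1 are not the same quantity. A patient with stable disease at week 13 is a non-responder under 8.1. If she is then debulked and a later scan shows little or no target disease, an unrestricted best response could make her a CR or PR. No section excludes post-surgery scans from the response count, and none says how a resected target lesion is scored.

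The reported rate and its confidence limits are at stake, because part of the count could reflect the operation rather than the drugs. Surgery is discretionary in an unblinded single-arm trial, so the share affected would depend on physician choice. If the same count were used for the 25-of-45 success rule, the false-positive rate would rise as well.

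**Working it through.** **Step 1: reproduce the design.** Inputs from 8.1 are p0 = .45, p1 = .65, alpha = beta = .10, 20 + 25 patients, and success at 25 or more of 45. An exact search for the optimal Simon design returns n1 = 20, continue at 10 or more, N = 45, success at 25 or more. Its alpha is .0903, its power .9001, and its probability of early termination at 45% is P(Bin(20, .45) ≤ 9) = .591. This matches "The probability of early termination if the response rate is 45% is .59".

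It does not match "In the first stage, 12 patients must have a response (PR or CR) in order to continue to the second stage". Continuing only at 12 gives early termination P(Bin(20, .45) ≤ 11) = .869, alpha .0533 and power .746. That mismatch is a separate matter for the sponsor to reconcile, so both boundaries are carried below.

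**Step 2: place the scans in time.**
- The week-13 scan falls at 91 ± 7 days, i.e. days 84-98, before surgery at weeks 15-16.
- Cycle 6 is at week 22, so the first scheduled post-surgery scan falls at weeks 22 + 4 to 22 + 6 = 26-28.
- The imaging section asks for confirmation of response at least 4 weeks later. For a response first seen at week 13 that means days 84 + 28 to 98 + 28 = 112-126 at the earliest, i.e. weeks 16-18, around or after surgery.

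**Step 3: size it under an assumption.** Let q be the share of all week-13 non-responders later scored CR or PR. The documents give no value for q. With a true 13-week rate of .45, the rate counted under a literal 8.2 is p2 = .45 + .55q.

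- *Final count only.* Stage 1 uses week-13 data: x ~ Bin(20, .45) must reach the boundary. Then y ~ Bin(20 − x, q) and z ~ Bin(25, p2), with success if x + y + z ≥ 25.
- *Both stages.* Every count uses p2: sum over x from the boundary to 20 of Bin(x; 20, p2) × P(Bin(25, p2) ≥ 25 − x).

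Probability of declaring success at a true 13-week rate of 45%:

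| q | rate by 8.2 | final only, ≥10/20 | final only, 12/20 | both stages, ≥10/20 | both stages, 12/20 |
|---|---|---|---|---|---|
| 0 | .450 | .090 | .053 | .090 | .053 |
| .02 | .461 | .112 | .062 | .117 | .070 |
| .05 | .4775 | .147 | .074 | .165 | .101 |
| .10 | .505 | .211 | .093 | .270 | .171 |
| .20 | .560 | .325 | .118 | .543 | .375 |

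When only the final count is affected, stage 1 caps the error whatever q is: 1 − .591 = .409 with 10 of 20, and 1 − .869 = .131 with 12 of 20.

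**Step 4: effect on the reported estimate.** Extra responders among 45 are 45 × .55 × .10 = 2.5, or 45 × .55 × .20 = 5.0. Five extra would move 20/45 = .444 (exact 90% limits .317 to .577) to 25/45 = .556 (.423 to .683), which meets the success criterion.

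**The case against.** The best defence is that 8.2 only supplies an estimator and an interval for an endpoint already defined in 8.1. With two scans in the window, best response reads naturally as the better of weeks 7 and 13. Section 3.1 treats the post-adjuvant scan as a new baseline, and the decision rules sit beside the 13-week definition. All of this stands as evidence of intent. It does not put the limit into 8.2, which is where the reported rate and its limits are specified.

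Three stronger readings are tempting, and the documents do not support them:

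- *That 8.2 overrides 8.1, so the false-positive rate is .27 or .54.* No section gives 8.2 precedence. Those figures need an assumed conversion rate, surgical clearance scored as response, and stage 1 also using post-surgery scans. No section says stage 1 waits for them. The same holds for .17 or .38 with 12 of 20.
- *That the bias can only be upward.* This is true for unconfirmed responses, since an added scan cannot lower a best response. If best response means confirmed response, a PR first seen at week 13 and not confirmed later would drop out, and the count could fall below the unconfirmed week-13 count.
- *That requiring confirmation would oblige the sponsor to recalculate power.* The documents do not say whether the 45% and 65% rates refer to confirmed responses, so this cannot be settled from them.

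**Conclusion.** The inconsistency is real and should be fixed before analysis. Applied as written, 8.2 can give a different count from the 13-week endpoint, and for unconfirmed responses that count can only be higher. Confidence is high on the missing limit and low on its effect, because no conversion rate is given and the scoring of resected lesions is not stated.

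Under the illustrative 10% or 20% conversion, the reported rate is overstated by about 5 or 11 percentage points (.505 or .560 against .450). The effect on the decision depends on the stage 1 boundary and on which counts are affected. With the printed 12 of 20 and only the final count affected, the error stays near the design alpha of .10. With 10 of 20 it exceeds .10 even at 2% conversion (.112).

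**What to change.** In Section 8.2, define the primary response rate as CR or PR by RECIST 1.1 on scans up to and including the week-13 pre-surgery scan. State that the same count is used for the stage 1 and 25-of-45 rules, and that scans after debulking are excluded from it. This wording would count a week-7 response followed by progression at week 13; if that is not intended, say so.

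As a secondary clarification, state whether the 4-week confirmation instruction under Tumor Imaging During the Study applies to the primary endpoint. If it does, say how a response first seen at week 13 is handled when its confirming scan falls around or after surgery.

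The time limit is a change of wording only: no new scans, visits or patients, and no change to N, alpha or power. The price is that the reported rate may be slightly lower than a best response taken over all scans.

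### A declared success at 25 or 26 responders of 45 would be reported with an exact 90% interval that still contains the 45% null rate, because section 8.2 does not tie the interval to the decision rule in section 8.1.

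*Combined protocol and SAP*

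**What the plan says.** Section 8.1 sets the decision rule. The contrast of interest is stated as "An increase from 45% to 65% among response-evaluable patients would be of sufficient interest". The design is given as "An optimal Simon two stage design with $\alpha = \beta = .10$ has been selected", and it "will require 20 patients in the first stage and 25 in the second". The trial succeeds if it reaches the second stage and "there are 25 or more patients with an objective response among the total of 45 treated". The section prints a stage-1 hurdle, "In the first stage, 12 patients must have a response (PR or CR) in order to continue to the second stage", and an operating characteristic, "The probability of early termination if the response rate is 45% is .59".

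Section 8.2 sets the reporting. "The objective response rate (ORR) will be estimated by the proportion of subjects" whose best response is complete or partial, "with corresponding exact 90% confidence limits being reported". It names no method behind the word exact. It gives no one-sided bound and no p-value, and does not mention the interim stop. It does not say how the limits relate to the count of 25. Nothing elsewhere in the document fills these gaps.

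**The concern.** For a single-arm trial judged against a fixed historical rate, readers will compare the lower confidence limit with 45%. If the rule says success and the limit lies below 45%, the report carries two messages on the primary endpoint: efficacy shown, and data compatible with no improvement. This happens at the smallest winning counts, where readers lean most on the interval. If the plan does not settle which statement governs, that choice is left until the result is known.

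**Working it through.** **Inputs.** From section 8.1: null rate p0 = .45, target rate p1 = .65, stage sizes n1 = 20 and n2 = 25, N = 45, success at 25 or more, alpha = beta = .10, probability of early termination (PET) .59 at p0. From section 8.2: raw proportion, exact 90% limits. Two readings are inferred. The rule is one-sided, because it has only an upper success boundary. The interval is two-sided Clopper-Pearson, with 5% per tail.

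**Step 1: reproduce the design.** With X1 ~ Bin(20, p), X2 ~ Bin(25, p) and continuation at X1 ≥ c:

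PET = P(X1 ≤ c − 1)

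P(success) = Σ over x1 ≥ c of P(X1 = x1) · P(X2 ≥ 25 − x1)

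| Continue at | PET at .45 | Alpha (p = .45) | Power (p = .65) |
|---|---|---|---|
| ≥ 10 of 20 | .591 | .0903 | .900 |
| ≥ 12 of 20 (as printed) | .869 | .053 | .746 |

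A search over designs for the smallest expected sample size at p0, with alpha and beta at most .10, returns n1 = 20, continue at ≥ 10, N = 45, success at ≥ 25. So N, the 25/45 rule, alpha = beta = .10 and PET .59 all belong to a cut-off of 10. The printed 12 does not.

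**Step 2: the planned interval.** The lower limit L solves P(X ≥ x | n = 45, L) = .05. The upper limit U solves P(X ≤ x | n = 45, U) = .05.

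| Responders | Proportion | 90% limits | Contains .45? | Rule in 8.1 |
|---|---|---|---|---|
| 25/45 | .556 | .423 to .683 | yes | success |
| 26/45 | .578 | .445 to .703 | yes | success |
| 27/45 | .600 | .467 to .723 | no | success |

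These limits do not depend on the stage-1 cut-off.

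**Step 3: which cause matters.** The two-stage exact lower limit solves P(X1 ≥ c and X1 + X2 ≥ x | L) = tail area. With c = 10:

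| Lower limit | 24/45 | 25/45 | 26/45 |
|---|---|---|---|
| As planned (Clopper-Pearson, 5% tail) | .401 | .423 | .445 |
| Method changed only (two-stage, 5% tail) | .408 | .427 | .447 |
| Level changed only (Clopper-Pearson, 10% tail) | .427 | .4493 | .471 |
| Both changed (two-stage, 10% tail) | .435 | .454 | .474 |

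Changing the method alone clears neither count. Changing the level alone clears 26 and leaves 25 short by .45 − .4493 = .0007. Changing both puts the limit above .45 at 25 and below it at 24, which is the decision rule. The two-stage p-value, P(X1 ≥ 10 and X1 + X2 ≥ x) at p = .45, is .0903 at 25 and .138 at 24.

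**Step 4: how often the conflict arises (c = 10).** The chance of finishing on exactly 25 or 26 is .0608 at p = .45, out of .0903 for all successes: .0608/.0903 = 67%. At p = .65 it is .1071 out of .9001: 12%.

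**Step 5: coverage and bias (c = 10).** Summed over both stages, on a grid of .0025 from .40 to .70, coverage of the nominal 90% interval runs from .893 to .953. Bias of the raw proportion over all trials is −.024 at p = .45 and −.007 at p = .65.

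**The case against.** The strongest reply is that nothing goes wrong with the decision. Section 8.1 alone defines success. Section 8.2 uses the interval to estimate and assigns it no comparison with 45%. A two-sided 90% interval beside a one-sided .10 rule is a common convention, and the two conflict only if a reader treats the interval as a second test. This stands as far as error rates go: alpha and power belong to the rule and do not change. It does not remove the reporting problem, because the plan is silent on how the two should be read together.

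A reader might infer more than the documents support:

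- *That the trial tests at half its design alpha, or that type I error is wrong.* The interval is not the decision rule, so neither follows.
- *That ignoring the two-stage sampling is the main fault.* Step 3 shows that the level does most of the work. The word exact could even mean a two-stage method, but with a cut-off of 10 a two-stage 90% interval still contains 45% at both counts.
- *That coverage is materially wrong.* It is close to nominal. Single-stage Clopper-Pearson at n = 45 already covers .904 to .947 over the same range, so most of the departure from .90 is ordinary discreteness.
- *That the raw proportion understates every reported result.* The negative bias averages in trials stopped at 20 patients. Among trials that reach stage 2 the raw proportion is too high, by .048 at 45% and .006 at 65%.

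One further objection stands in full: the adjusted figures need a cut-off of 10, not the printed 12. Under 12, the two-stage one-sided 90% lower limit is .477 at 25/45, but it also exceeds .45 at 23/45 (.454) and 24/45 (.465), which are failures under the rule. The conflict would then run the other way.

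**Conclusion.** The concern holds as an inconsistency in the reported inference for the primary endpoint. As planned, 25/45 and 26/45 are successes whose 90% interval includes 45%, whichever stage-1 cut-off applies. With continuation at 10 or more of 20, these counts are two thirds of successes when the treatment does no better than 45%, and about one in eight when the true rate is 65%. The main cause is the mismatch of levels; the interim stop accounts for the last .0007 at 25/45.

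This rests on two inferences, that the rule is one-sided and that exact limits means two-sided Clopper-Pearson. It does not touch the validity of the 25/45 rule. It merits correction in the SAP before results are known, and does not call for redesign.

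**What to change.** 1. Reconcile the stage-1 cut-off in section 8.1. The printed 12 and the stated PET of .59 cannot both be right; .59 and alpha = beta = .10 correspond to continuing at 10 or more. The adjusted figures should not be fixed until this is settled.
2. In section 8.2, state that the 25/45 rule governs the conclusion.
3. Report with it the two-stage exact p-value and the matching one-sided 90% lower limit, which is the lower end of a two-stage exact 80% interval. With a cut-off of 10 these are p = .0903 and .454 at 25/45, against a limit of .435 at 24/45, so limit and rule agree.
4. Keep the raw proportion and the two-sided 90% interval, labelled as descriptive. The two-stage unbiased estimate (UMVUE), .581 at 25/45 with a cut-off of 10 against the raw .556, is an optional supplement.

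The cost is SAP wording and a few lines of code, with no new patients or data. The downside is a little more analysis and a second interval to explain.

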4.1.2 Preclinical and Clinical Trial Data and Rationale

Solid evidence to date demonstrates that the immune system plays an important role in the development and progression of OC, and can influence the disease outcome. Early studies reported that CD3+ TILs were present in 55% of OC and the presence of TILs was correlated with improved clinical prognosis ²⁷. BRCA1-deficient tumors exhibit higher neoantigen load and have particularly high numbers of TILs, partly explaining the superior outcome in these patients ^{28,29}. Improved prognosis is mostly attributable to cytotoxic CD8+ TILs, while intra-tumoral Tregs, macrophages, and immature myeloid cells appear to confer a worse prognosis ^{11,30}. Understanding OC as an immunogenic tumor supports efforts to harness immunotherapeutic strategies to further improve prognosis. The challenge remains to determine which patients will benefit from immunotherapies and to identify how immunotherapy should be incorporated into the OC standard of care. In addition, most of the studies targeting the tumor microenvironment have primarily focused on the primary tumor, and much less is known about recurrent disease. Despite an initial response to standard treatment with aggressive surgical debulking and platinum/taxane drug combination, ovarian tumors invariably recur and patients ultimately die of platinum-resistant disease.

This project focuses on the tumor microenvironment in recurrent disease. Our approach stems from (i) significant expertise of the Principal Investigator (PI) in IP chemotherapy and IP immunotherapy with immune modulators ³¹⁻³⁴, (ii) our recent results from a phase I trial using cisplatin/rintatolimod combination in recurrent OC, (NCT02432378); and (iii) significant preclinical data from co-investigators on the in vivo efficacy of cisplatin/aPD1 combination in our new OC animal models ⁶.

Intraperitoneal administration of immune modulators provides clinical benefit for OC patients.

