5.1.1 Participant Inclusion Criteria

Participants are eligible to be included in the study only if all of the following criteria apply:

- 1. Patients must be at least 18 years of age on the day of signing informed consent.
- 2. Patients must have first or second peritoneal recurrence of epithelial adenocarcinoma or carcinosarcoma of ovarian, tubal or peritoneal origin:
 - a. Histologic documentation of the original primary tumor is required via the pathology report.
 - b. Original tumor blocks from the primary diagnosis will be requested by our study pathologist at Magee-Women's Hospital of UPMC Cancer Centers if the patient did not have their initial surgery at Magee. Original tumor blocks may be reviewed after registration (informed consent and enrollment). Tumor block should be held until study is completed.
 - 3. Patients must have completed prior platinum-based therapy. Response can be complete or partial if it otherwise meets platinum sensitive criteria, see below.
 - 4. Patients must be platinum-sensitive, defined as having a progression free interval (PFI) of more than 6 months (180 days) from any platinum therapy. Patients are allowed to have had other lines of therapy since last platinum if PFI after platinum therapy meets platinum sensitive criteria.
 - 5. Patients must have measurable disease in the peritoneal cavity, measurable per RECIST 1.1 criteria:
 - a. A mass with a length of 1.0 cm or greater and/or
 - b. A lymph node with a length of 1.5 cm or greater in the shortest axis.

- 6. Patients must be a reasonable candidate for laparoscopy and IP platinum regimen with no prior evidence of clinically significant intra-abdominal adhesions, persistent abdominal wall infections, renal toxicity or bowel obstruction.
- 7. Patients of childbearing potential must:
 - a. Have a negative pregnancy test prior to the study entry.
 - b. Must discontinue breastfeeding prior to the first date of treatment on this study if applicable.
 - c. Agree to follow the contraceptive guidance in Appendix 3 during the treatment period and for at least 120 days after the last dose of study treatment.
- 8. Patients must agree to the protocol designated clinical monitoring to receive the study regimens.
- 9. The participant provides written informed consent for the trial.
- 10. Have an Eastern Cooperative Oncology Group (ECOG) performance status of 0 to 1. Evaluation of ECOG is to be performed within 28 days prior to the date of allocation/randomization.

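### The immune-response associations are adjusted for time since diagnosis but not for progression-free interval since platinum or recurrence number, so a marker of platinum sensitivity could be read as evidence for the immune mechanism.

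*Combined protocol and SAP*

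**What the plan says.** Under the secondary analyses in Section 8.2, "The panel of immune parameters will be tested for association with objective response with the Jonckheere-Terpstra test for trend", with response ordered PD, SD, PR, CR. Then: "Significant association will be adjusted for initial tumor grade, and the interval between initial diagnosis of OC and protocol accrual". Multiplicity is handled separately: "To guard against false positive results, the estimated false discovery rate will be calculated by the method of Benjamini and Hochberg". The adjustment is therefore a second step, applied only to associations that are already significant. No model is named for it, and the Jonckheere-Terpstra test takes no covariates.

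Three eligibility rules in Section 5.1.1 bear on the choice of covariate:

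- "Patients must be platinum-sensitive, defined as having a progression free interval (PFI) of more than 6 months (180 days) from any platinum therapy". There is no upper limit.
- "Patients must have first or second peritoneal recurrence of epithelial adenocarcinoma or carcinosarcoma".
- "Patients are allowed to have had other lines of therapy since last platinum if PFI after platinum therapy meets platinum sensitive criteria".

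Elsewhere PFI appears only as an outcome: Section 3.1 plans a ratio of the on-trial interval to the patient's initial one. Section 5.4 plans no stratification. No section names PFI, recurrence number or prior lines as covariates.

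**The concern.** Cisplatin is given in every cycle (Section 5.2.1). Section 8.1 takes the response rate to intraperitoneal cisplatin alone as about 45%, and the anticipated-results text in Section 3.3 expects responses because the disease is platinum-sensitive. How sensitive a patient is to platinum is therefore a likely driver of response, and PFI is the protocol's own measure of it.

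If an immune marker is also related to platinum sensitivity, marker and response will be associated through that common cause. Section 4.1.2 makes such a relation plausible for tumor-infiltrating lymphocytes: "the presence of TILs was correlated with improved clinical prognosis". Adjusting for an imperfect stand-in for PFI removes only part of this association. The Benjamini-Hochberg step does not help, because it controls chance findings and not confounding.

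What is at stake is interpretation. The trial sets out to test whether the combination works through type 1 immunity (Sections 3.1 and 3.3). A marker that carries no more than platinum sensitivity could be reported in support of that mechanism.

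**Working it through.** The plan gives no sample size, power or error rate for this association, so there is no figure of its own to reproduce. The check has two parts.

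**1. What the planned covariate measures.** Let T be the time from diagnosis to accrual.

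- First recurrence: T = first treatment + PFI.
- Second recurrence: T = first treatment + first interval + second treatment + last PFI, plus any later non-platinum lines.

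Hypothetical example, assuming 6 months for first treatment and 5 for the second:

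- A first-recurrence patient with PFI 24 months has T = 6 + 24 = 30.
- A second-recurrence patient with a first interval of 12 and a last PFI of 7 has T = 6 + 12 + 5 + 7 = 30.

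The two patients have equal T and very different PFI. Within either recurrence group T still rises with PFI. It is the mixing of groups that breaks the link.

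**2. How much spurious association is left.** Both simulations below use n = 45 (the maximum in Section 8.1), four response classes and a two-sided 5% level. Tests are rank-based correlations, partial where adjusted. The marker has no link to response except through platinum sensitivity, observed as PFI. Tumor grade is not modelled. None of the strengths of association, nor the recurrence mix, comes from the documents.

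*(a) Strong links.* Marker and latent response each load 0.4 to 0.7 on platinum sensitivity. Successive intervals correlate 0.5 on the log scale. There were 3,000 runs per setting. Entries are percentages of trials with a significant association, over the range of loadings; Two-step means significant both unadjusted and after adjusting for T.

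| Share at second recurrence | Spearman T, PFI | Unadjusted | Adjusted for T | Two-step | Adjusted for PFI |
|---|---|---|---|---|---|
| 0% | 1.0 (by construction) | 14.1-88.1 | 5.1-5.8 | 2.5-4.3 | 5.1-5.8 |
| 50% | about 0.55 | 14.8-88.1 | 10.5-65.7 | 9.9-65.6 | 5.0-5.8 |
| 100% | about 0.84 | 16.1-87.6 | 6.3-23.3 | 5.5-23.3 | 4.7-5.8 |

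At a 50/50 mix the mean spurious rank correlation falls from 0.14-0.44 unadjusted to only 0.10-0.35 after adjusting for T. After adjusting for PFI it is 0.01-0.02.

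*(b) Moderate links.* Marker-PFI correlation is .3 to .5, the odds ratio for response is 2 to 3 per SD of log PFI, and one third to one half of patients are at second recurrence. For the single tests (6,000 runs per scenario):

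| Setting | Unadjusted | Adjusted for T | Adjusted for PFI |
|---|---|---|---|
| correlation .3, odds ratio 2 | 10% | 7.5-7.8% | 5% |
| correlation .5, odds ratio 3 | 35% | 21-26% | 5% |

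Under the two-step rule that Section 8.2 describes, the range is roughly 6-22%. With PFI and recurrence number added it is about 5%, the nominal level; also requiring prior unadjusted significance can only lower that. The excess is therefore about 6 - 5 = 1 to 22 - 5 = 17 percentage points.

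PFI restores the nominal level here because it is assumed to capture platinum sensitivity exactly. In practice the correction would be less complete.

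**The case against.** The strongest objection concerns meaning. Cisplatin is part of the regimen, so a marker of platinum sensitivity is a true correlate of response to it, and Section 8.2 promises only an assessment of association. This stands. A reader might infer that such markers would be false correlates of response; the documents do not support that. The risk is limited to crediting the association to rintatolimod and pembrolizumab. Nor would adjusting for PFI isolate their effect, because a single-arm trial cannot separate it from the platinum effect.

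Second, the marker-PFI link is not documented. Section 4.1.2 relates lymphocytes to prognosis, not to PFI, and notes that recurrent disease is less studied. The planned markers include cells in resected residual tumor, taken after four cycles, which is not a baseline measure. The entry threshold also removes the least platinum-sensitive patients. All this stands, and it is why the size can only be given conditionally. At the low end the excess is about one percentage point.

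Third, a reader might infer that time since diagnosis says almost nothing about PFI at second recurrence. That goes too far: T contains the last PFI, and the rank correlation is about 0.84 when all patients are at second recurrence and successive intervals correlate 0.5. The weakness lies in mixing first and second recurrences without a term for it, which also means there is no need to drop the planned covariate.

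What the objections do not remove is that the protocol's own measure of platinum sensitivity is absent from the one analysis where it is an obvious confounder.

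**Conclusion.** The concern holds as a limited one. In a mixed population, grade and time since diagnosis adjust only partly for platinum sensitivity. Under moderate assumed links the planned two-step rule gives roughly 6-22% spurious associations, against about 5% with PFI and recurrence number added. Stronger assumed links give more, and a population almost entirely at first recurrence gives nearly no excess. The documents give neither the recurrence mix nor the marker-PFI correlation, so no single figure can be defended.

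A reader might also infer that the trial's efficacy conclusion is at risk. It is not: the two-stage response-rate decision uses none of these covariates, and this analysis is secondary. The change is a cheap improvement.

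**What to change.** In Section 8.2:

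- Keep initial tumor grade and the diagnosis-to-accrual interval. Add PFI from the most recent platinum, on the log scale, and recurrence number (first or second).
- Define that PFI explicitly by its start and end dates. Section 5.1.1 sets a threshold relative to any platinum therapy, and Section 2.1 speaks of a treatment-free interval, so neither fixes the quantity to record.
- Keep the Jonckheere-Terpstra test as the unadjusted test, and name an ordinal regression, such as proportional odds, for the adjusted step.
- Word conclusions as association with response to the combined regimen, and state that the design cannot attribute it to the immune components.

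The cost is SAP wording and one or two degrees of freedom. PFI has to be established against the entry threshold, and Section 7.1.1.5.2 already reviews all prior cancer treatments, so little or no new data collection should be needed; the case report form should nevertheless hold the dates. The loss of precision is small at 45 patients but larger for resected tumor. Interval surgery is discretionary, and Section 3.3 reports that two thirds completed it in the predecessor trial. The same share here would leave about 45 x 2/3 = 30 patients.
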